2.3. Statistical Hypotheses

No formal hypotheses will be tested for this study. An estimation approach will be used to evaluate the effect of hepatic impairment (i.e., moderate and potentially either mild or severe) on the PK of daprodustat. The primary comparisons of interest are the single dose PK parameters, including Cmax and AUC of daprodustat in each hepatic impaired cohort compared to the normal hepatic function cohort.

The point estimates of the geometric least squares (GLS) mean ratio for the PK parameters and associated 90% confidence intervals (CIs) will be provided for cohort comparisons (hepatically impaired : healthy participants). The PK parameters will be log-transformed prior to analysis and cohort comparisons will be expressed as ratios on the original scale. %AUCex and Tmax and will be summarized descriptively.

3. PLANNED ANALYSES

3.1. Interim Analyses

An informal interim analysis of the primary endpoints AUC (0- ∞), AUC(0-t) and C_{max} will be conducted following completion of Part 1 of the study, with possible progression to Part 2 based on the following criteria:

- If a < 2-fold change in daprodustat exposure (AUC) is observed in participants with moderate hepatic impairment compared to healthy matched control group, the study may enrol participants with severe hepatic impairment and a healthy, matched control group.
- If a \geq 2-fold change in daprodustat exposure (AUC) is observed in participants with moderate hepatic impairment compared to healthy matched control group, the study may enrol participants with mild hepatic impairment and a healthy, matched control group.

3.2. Final Analyses

The final planned primary analyses will be performed after the completion of the following sequential steps:

1. All participants have completed the study as defined in the protocol.
2. All required database cleaning activities have been completed and final database release and database freeze has been declared by Data Management.

4. ANALYSIS POPULATIONS

Population	Definition / Criteria	Endpoint(s) Evaluated
Screened Population	
 All participants who were screened will be considered for this population. This population will be used for summarizing screening status. 	
 Screen Failure
Enrolled Population	
 All participants who were successfully screened and enrolled for the trial and for whom a record exists on the study database. This population will be used for summarize number of subjects by Country and Site ID and age ranges. 	
 Study Population
Safety Population	
 All participants who received at least one dose of study medication. This will be the primary population for the safety analyses. 	
 Study Population Safety
PK Population	
 All participants in the 'Safety Population' for whom a PK sample has been obtained and analyzed will be included in the PK population. This population will be used in the evaluation of PK data. PK samples that may be affected by protocol deviations will be reviewed by the study team to determine whether or not the sample will be excluded from the analyses of PK data. 	
 PK
PD Population	
 All participants in the 'Safety Population' who had at least 1 PD assessment. PD samples that may be affected by protocol deviations will be reviewed by the study team to determine whether or not the sample will be excluded from the analyses of PD data. 	
 PD

NOTES:

- Please refer to [Appendix 10](#) which details the population to be used for each display being generated.

4.1. Protocol Deviations

- Important protocol deviations (including deviations related to study inclusion/exclusion criteria, conduct of the trial, participant management or participant assessment) will be summarized and listed.
- Protocol deviations will be tracked by the study team throughout the conduct of the study in accordance with the Protocol Deviation Management Plan.
 - Data will be reviewed prior to freezing the database to ensure all important deviations and deviations which may lead to exclusion from the analysis are captured and categorized on the protocol deviations dataset.
 - This dataset will be the basis for the summaries and listings of protocol deviations.
- A separate listing of all inclusion/exclusion criteria deviations will also be provided.

5. CONSIDERATIONS FOR DATA ANALYSES AND DATA HANDLING CONVENTIONS

Table 1 provides an overview of appendices within the RAP for outlining general considerations for data analyses and data handling conventions.

Table 1 Overview of Appendices

Section	Component
10.1	Appendix 1: Protocol Deviation Management
10.2	Appendix 2: Time & Events
10.3	Appendix 3: Treatment States
10.4	Appendix 4: Data Display Standards & Handling Conventions
10.5	Appendix 5: Derived and Transformed Data
10.6	Appendix 6: Premature Withdrawals & Handling of Missing Data
10.7	Appendix 7: Values of Potential Clinical Importance
10.8	Appendix 8: Model Checking and Diagnostics for Statistical Analyses.

6. STUDY POPULATION ANALYSES

6.1. Overview of Planned Analyses

The study population displays will be based on the “Safety” population, unless otherwise specified.

Table 2 provides an overview of the planned study population displays, with full details of data displays being presented in Appendix 10: List of Data Displays.

Table 2 Overview of Planned Study Population Analyses

Display Type	Data Displays Generated	
	Table	Listing
Subject Disposition		
Subject Disposition	Y	
Reasons for Screening Failures ^[1]	Y	Y
Reasons for Withdrawals		Y
Important Protocol Deviations	Y	Y
Inclusion and Exclusion Criteria Deviations		Y
Demography		
Demographic Characteristics	Y	Y
Race & Racial Combinations	Y	Y
Study Populations	Y	Y
Summary of Number of Subjects by Country and Site ID	Y	
Summary of Age Ranges	Y	
Summary of Child-Pugh score	Y	Y
Medical/Surgical History & Concomitant Medications		
Medical/Surgical History		Y
Concomitant Medication	Y	Y
Exposure and Treatment Compliance		
Exposure to Study Treatment		Y

NOTES:

- Y = Yes display generated.

[1] Conditional displays, if data is available table and listing will be generated.

7. PRIMARY STATISTICAL ANALYSES

7.1. Interim Analyses

An informal interim analysis of the primary PK endpoints AUC (0- ∞), AUC(0-t) and C_{max} will be conducted following completion of Part 1 of the study, with possible progression to Part 2 based on the following criteria:

- If a < 2 -fold change in daprodustat exposure (AUC) is observed in participants with moderate hepatic impairment compared to healthy matched control group, the study may enrol participants with severe hepatic impairment and a healthy, matched control group.
- If a ≥ 2 -fold change in daprodustat exposure (AUC) is observed in participants with moderate hepatic impairment compared to healthy matched control group, the study may enrol participants with mild hepatic impairment and a healthy, matched control group.

7.2. Pharmacokinetic Analyses

The reconciliation of the PK Case Report Form (CRF) and SMS2000 data will be performed by, or under the direct auspices of Clinical Pharmacology Sciences and Study Operations (CPSSO), GlaxoSmithKline.

The merge of PK concentration data and CRF data will be performed by PPD Programming under the direct auspices of Clinical Programming, GlaxoSmithKline.

Derivation of PK parameters will be performed by PPD PK group under the direct auspices of Clinical Pharmacology Modelling and Simulation (CPMS), GlaxoSmithKline.

Statistical analysis of PK data and parameters will be performed by PPD Statistics and Programming under the direct auspices of Clinical Statistics, GlaxoSmithKline.

7.2.1. Overview of Planned Pharmacokinetic Analyses

The PK analyses will be based on the PK population, unless otherwise specified.

[Table 3](#) provides an overview of the planned non-compartmental PK analyses of daprodustat and its six metabolites, (GSK2391220 (M2), GSK2506104 (M3), GSK2487818 (M4), GSK2506102 (M5), GSK2531398 (M6) and GSK2531401 (M13)) with full details being presented in [Appendix 10](#): List of Data Displays.

Table 3 Overview of Planned Pharmacokinetic Analyses

Display Type	Untransformed							Log-Transformed						
	Stats Analysis			Summary		Individual		Stats Analysis			Summary		Individual	
	T	F	L	T	F	F	L	T	F	L	T	F	F	L
PK Concentrations				Y ^[3]	Y ^[1] ^[2]	Y ^[1]	Y ^[3]							
Plasma PK Parameters	Y ^[4]			Y			Y	Y ^[4]		Y	Y			

NOTES :

- T = Table, F = Figure, L = Listings, Y = Display generated.
- Stats Analysis = Represents TFL related to any formal statistical analyses (i.e. modelling) conducted.
- Summary = Represents TFL related to any summaries (i.e. descriptive statistics) of the observed raw data.
- Individual = Represents FL related to any displays of individual subject observed raw data.

^[1] Linear and Semi-Logarithmic plots will be created on the same display.

^[2] Separate mean and median plots will be generated.

^[3] Unbound PK Concentrations for Daprodustat and its metabolites will be summarized on a separate display.

^[4] Supportive SAS Output from Statistical Analysis.

7.2.1.1. Drug Concentration Measures

Refer to [Appendix 4: Data Display Standards & Handling Conventions \(Section 10.4.3. Reporting Process & Standards\)](#).

7.2.1.2. Pharmacokinetic Parameters**7.2.1.2.1. Deriving Pharmacokinetic Parameters**

- Refer to [Appendix 4: Data Display Standards & Handling Conventions \(Section 10.4.3. Reporting Process & Standards\)](#).
- Plasma concentration-time data for daprodustat and its six predominant metabolites will be analysed by non-compartmental methods according to current working practices with WinNonlin 6.4 or higher.
- Non-compartmental analysis will be performed in accordance with GSK PK Guidance document GUI_51487.
- All calculations of non-compartmental parameters will be based on actual sampling times recorded during the study.
- PK parameters described in [Table 4](#) will be determined from plasma concentration-time data as data permits.

Table 4 Derived Pharmacokinetic Parameters

Parameter	Parameter Description
AUC(0-t)	Area under the concentration-time curve from time zero to the time of the last quantifiable concentration (C(t)) will be calculated using the linear trapezoidal rule for each incremental trapezoid and the log trapezoidal rule for each decremental trapezoid (daprodustat and its six metabolites).
AUC(0-∞)	Area under the concentration-time curve extrapolated to infinity calculated as: $\text{AUC}(0-\infty) = \text{AUC}(0-t) + C(t) / \lambda_{z}$ (daprodustat and its six metabolites) where C(t) is the last measurable concentration.
%AUCex	The percentage of AUC (0-∞) obtained by extrapolation (%AUCex) will be calculated as: $[\text{AUC}(0-\infty) - \text{AUC}(0-t)] / \text{AUC}(0-\infty) \times 100$ (daprodustat and its six metabolites)
Cmax	Maximum observed plasma concentration, determined directly from the concentration-time data. (daprodustat and its six metabolites)
Lambda_z	The first order rate constant associated with the terminal (log-linear) portion of the concentration-time curve. (daprodustat and its six metabolites)
Tmax	Time to reach Cmax, determined directly from the concentration-time data. (daprodustat and its six metabolites)
t _{1/2}	Apparent terminal phase half-life will be calculated as: $t_{1/2} = \ln 2 / \lambda_{z}$ (daprodustat and its six metabolites)
fu	Unbound fraction (fu) of daprodustat and its metabolites will be calculated using the total and unbound plasma concentration of daprodustat and its metabolites generated at 3, 12 and 24 h post dose for both normal and hepatic impaired participants using the following formula: $F_u = C_{unbound} / C_{total}$
free AUC(0-t)	AUC(0-t) * fu (daprodustat)

Parameter	Parameter Description
free AUC(0-∞)	AUC(0-∞) * fu (daprodustat)
free Cmax	Cmax * fu (daprodustat)

7.2.1.2.2. Statistical Analysis of Pharmacokinetic Parameters

For each of the parameters AUC (AUC(0-∞), AUC (0-t) and %AUCex)-total and free, t_{1/2}, T_{max} and C_{max}-total and free the following summary statistics will be calculated and tabulated by each cohort:

- **Untransformed Data:** N, n, arithmetic mean, 95% confidence interval (CI) for the arithmetic mean, SD, median, minimum and maximum.
- **Log_e-transformed Data:** Geometric mean, 95% CI for the geometric mean, SD of log_e-transformed data and between subject geometric coefficient of variation (%CVb).
- If data suggest appreciable differences existing in the results obtained based on the observed total and unbound daprodustat PK plasma concentration data, and if deemed appropriate, the bound fraction (1-Fu) at 3 h, 12 h and 24 h will be analysed using paired t-test comparing 12h versus 3h, 24 h versus 3h and 24 h versus 12h.

The following PK statistical analyses will only be performed, if sufficient data is available (i.e. if subjects have well defined plasma profiles). Pharmacokinetic analysis and Statistical analyses of the PK parameter data will be the responsibility of PPD.

Planned Pharmacokinetic Statistical Analyses
Endpoint(s)

 • Plasma primary PK endpoints include AUC (0-t), AUC (0-∞), Cmax and t_{1/2}, as data permit
Model Specification

 • The log-transformed AUC(0-t), AUC (0-∞), Cmax and t_{1/2} values for daprodustat and metabolites will be analyzed separately using analysis of variance (ANOVA) as appropriate to the study design, fitting a fixed effect term for cohort. Point estimates and 90% CIs for the differences of interest (hepatically impaired versus healthy participants) will be constructed using the residual variance.
Model Checking & Diagnostics

 • Refer to Appendix 8 : Model Checking and Diagnostics for Statistical Analyses.
Model Results Presentation

 • Statistical analysis by ANOVA will be presented in tabular format with geometric mean ratios for the hepatically impaired versus healthy participants and 90% CI for the ratios of AUC (0-t), AUC (0-∞), Cmax and t_{1/2} for daprodustat and metabolites.

Planned Pharmacokinetic Statistical Analyses
Endpoint(s)

 • Tmax
Model Specification

 • If data permit, Tmax will be analyzed nonparametrically using the Mann Whitney U test (Wilcoxon rank sum test). The point estimates and 90% CI for the median differences will be derived for hepatic impairment and healthy participants based on Hodges-Lehmann estimation.
Model Checking & Diagnostics

 • Refer to Appendix 8: Model Checking and Diagnostics for Statistical Analyses.
Model Results Presentation

 • The point estimates and 90% confidence intervals for the median differences will be calculated for the cohort difference (hepatically impaired – healthy participants).

Sensitivity Pharmacokinetic Statistical Analyses
Endpoint(s)

 • AUC(0-t), AUC(0-∞), Cmax and t1/2
Model Specification

 • The log-transformed AUC(0-t), AUC(0-∞), Cmax and t½ values for daprodustat and metabolites will be analyzed separately using analysis of covariance (ANCOVA) as appropriate to the study design, fitting fixed effect terms for cohort, gender, age and BMI. Point estimates and 90% CIs for the differences of interest (hepatically impaired versus healthy participants) will be constructed using the residual variance.
Model Checking & Diagnostics

 • Refer to Appendix 8: Model Checking and Diagnostics for Statistical Analyses.
Model Results Presentation

 • Statistical analysis by ANCOVA will be presented in tabular format with geometric mean ratios for the difference between participants with hepatic impairment and healthy participants, and 90% CI for the ratios of AUC(0-t), AUC(0-∞), Cmax and t½ for daprodustat and metabolites.

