1.1. RAP Amendments

RAP Section	Amendment Details
Reporting and Analysis Plan_Study200231_Final_V1 [22-Nov-2017]	
Reporting and Analysis Plan_Study200231_Amendment_Final_V1 [Insert Date]	
Section 2.1	
 • Second primary objective and associate endpoint adds daprodustat AND its metabolites to plasma protein binding and unbound concentration in plasma. • Secondary PD endpoint is revised to say Cmax, EPO instead of Emax; and specifies AUC(0-t, EPO) instead of AUC(last)
Section 10.9.1	
 • Cmax, EPO added
Section 7.2.1.2.2	
 • Added text determining if there is concentration-dependent protein binding. "If data suggest appreciable differences existing in the results obtained based on the observed total and unbound daprodustat PK plasma concentration data, and if deemed appropriate, the bound fraction (1-Fu) at 3 h, 12 h and 24 h will be analysed using paired t-test comparing 12h versus 3h, 24 h versus 3h and 24 h versus 12h".
Section 10.4.1	
 • Updated heading to match with latest updates in TA and TE. Removed Treatment in heading. Study Treatment & Display Descriptors to Study Displays Descriptors.
Section 10.7.1	
 • PCI laboratory values added for hepatic impairment subjects and updated units for Albumin and Creatinine.

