2. SUMMARY OF KEY PROTOCOL INFORMATION

2.1. Study Objective(s) and Endpoint(s)

Objectives	Endpoints

Primary Objectives
 
 To compare plasma PK parameters of daprodustat and its six metabolites (GSK2391220 (M2), GSK2506104 (M3), GSK2487818 (M4), GSK2506102 (M5), GSK2531398 (M6), and GSK2531401 (M13)) in participants with hepatic impairment to healthy controls matched in gender, age, and body mass index (BMI). To evaluate the impact of hepatic impairment on the plasma protein binding and unbound concentration of daprodustat and its metabolites in plasma. 	
Primary Endpoints
 
 Daprodustat and its metabolites plasma area under the concentration-time curve from time zero (pre-dose) extrapolated to infinite time [AUC (0-∞)], percentage of AUC(0-∞) obtained by extrapolation (%AUCex), time zero (pre-dose) to last time of quantifiable concentration [AUC(0-t)], maximum observed concentration (C_{max}) following a single oral dose of daprodustat, apparent terminal phase half-life (t_{1/2}), and time of occurrence of C_{max} (T_{max}) following a single oral dose of daprodustat. Unbound concentration and unbound fraction in plasma of daprodustat and its metabolites at 3, 12 and 24 h post dose (as data permit).

Secondary Objectives
 
 To characterize the effect of hepatic impairment on the PD effect of daprodustat. To assess the safety and tolerability of a single 6 mg dose of daprodustat. 	
Secondary Endpoints
 
 Maximum observed erythropoietin concentration (C_{max}, EPO), Time of the maximum observed erythropoietin concentration (T_{max}, EPO) and erythropoietin area under the concentration-time curve from time zero (pre-dose) to the last time of quantifiable concentration [AUC (0-t, EPO)]. Safety and tolerability parameters, including adverse events and clinical laboratory tests.

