
 Reporting for tables, figures and formal statistical analyses: 
 Planned time relative to dosing will be used in figures, summaries, statistical analyses and calculation of any derived parameters, unless otherwise stated. The impact of any major deviation from the planned assessment times and/or scheduled visit days on the analyses and interpretation of the results will be assessed as appropriate (see Section 4.1). Reporting for Data Listings: 
 Planned and actual time relative to study drug dosing will be shown in listings (Refer to IDSL Statistical Principle 5.05.1). Unscheduled or unplanned readings will be presented within the subject's listings. Visits outside the protocol defined time-windows (i.e. recorded as protocol deviations) will be included in listings but omitted from figures, summaries and statistical analyses. 	
Unscheduled Visits	

 Unscheduled visits will not be included in summary tables, unless otherwise stated. Unscheduled visits will not be included in figures. All unscheduled visits will be included in listings. 	
Descriptive Summary Statistics	
Continuous Data	Refer to IDSL Statistical Principle 6.06.1
Categorical Data	N, n, frequency, %
Reporting of Pharmacokinetic and Pharmacodynamic Concentration Data	
Descriptive Summary Statistics	Refer to IDSL Statistical Principle 6.06.1 and Standards for the Transfer and Reporting of PK and PD Data using HARP. For NQ values, refer to GUI_51487.
Reporting of Pharmacokinetic Parameters	
Descriptive Summary Statistics. (Log _e Transformed)	N, n, geometric mean, 95% CI of geometric mean, standard deviation (SD) of log transformed data and %CVb will be reported. $CVb (\%) = \sqrt{(\exp(SD^2) - 1)} * 100$ [NOTE: SD = SD of log _e transformed data]
Parameters Not Being Log _e Transformed	%AUCex and Tmax
Summary Tables	Cmax, Tmax, AUC(0-t), AUC (0-∞), t1/2, and %AUCex as data permit. The following PK parameters will not be summarised: first point, last point, and number of points used in the determination of λz.
Summary of Statistical analysis	Geometric mean ratio of hepatic impaired : healthy, point estimate and an associated 90% CI.

Reporting Standards	
Listings	Include PK Parameters C _{max} , T _{max} , AUC(0-t), AUC (0-∞), and t _{1/2} as data permit. Include the first point, last point and number of points used in the determination of λ _z .

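### The unbound fraction is a primary endpoint, but the SAP plans no impaired-versus-healthy fu ratio with a confidence interval

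*SAP*

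**What the plan says.** All references are to the amended SAP and Protocol Amendment 1.

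- **Endpoint.** SAP 2.1 lists as primary "Unbound concentration and unbound fraction in plasma of daprodustat and its metabolites at 3, 12 and 24 h post dose (as data permit"), under an objective about the effect of hepatic impairment on binding. Protocol section 4 agrees.
- **Derivation.** SAP Table 4 defines fu for daprodustat and its metabolites from total and unbound concentrations "generated at 3, 12 and 24 h post dose for both normal and hepatic impaired participants". It then defines free AUC(0-t), free AUC(0-∞) and free Cmax for daprodustat only, the last as "Cmax * fu (daprodustat"), with no time attached to fu.
- **Summaries.** The by-cohort list in SAP 7.2.1.2.2 covers AUC and Cmax (total and free), %AUCex, half-life and Tmax. The Summary Tables entry in SAP 10.4.3 is "Cmax, Tmax, AUC(0-t), AUC (0-∞), t1/2, and %AUCex as data permit". Neither names fu.
- **Cohort models.** The ANOVA lists log AUC(0-t), AUC(0-∞), Cmax and half-life. The sensitivity analysis takes the same four, whose "values for daprodustat and metabolites will be analyzed separately using analysis of covariance (ANCOVA"). The notes to Tables 3.7 and 3.8 add the three free parameters, but not fu.
- **Binding analysis.** This depends on an appreciable difference between the total and unbound daprodustat results and on a judgement that the test is suitable. The SAP's words are: "the bound fraction (1-Fu) at 3 h, 12 h and 24 h will be analysed using paired t-test comparing 12h versus 3h", with the other two pairs of times to follow. Table 3.10 displays this for daprodustat. SAP 1.1 gives its purpose: "Added text determining if there is concentration-dependent protein binding".
- **Priority.** SAP 2.3 states: "The primary comparisons of interest are the single dose PK parameters, including Cmax and AUC of daprodustat" in each impaired cohort against normal hepatic function.

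**The concern.** An endpoint meant to show what hepatic impairment does to binding needs a comparison of impaired with healthy participants. The one planned test compares a participant's bound fraction at one time with the same participant's at another. Even if run separately in each cohort, it answers a different question: whether binding changes with concentration.

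Followed as written, the plan produces no impaired:healthy fu estimate with a CI for any analyte. The free-exposure comparison does not fill the gap. It exists for daprodustat only, and it combines the change in total exposure with the change in binding. Protocol 10.4.1 defers the details of the fu analysis to the reporting and analysis plan, so the SAP is where the comparison should be stated.

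A smaller point is that free AUC and free Cmax use an fu measured at three times, and the SAP text does not say which one.

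**Working it through.** **1. Where fu appears**

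| Planned item | Parameters | Is fu the response? |
|---|---|---|
| Cohort ANOVA (7.2.1.2.2) | AUC(0-t), AUC(0-∞), Cmax, half-life | No |
| Cohort ANCOVA (7.2.1.2.2) | the same four | No |
| Tables 3.7 and 3.8, notes | the same four, plus free AUC(0-t), free AUC(0-∞), free Cmax | No |
| Tmax, Hodges-Lehmann | Tmax | No |
| Paired t-test, Table 3.10 | daprodustat 1 − fu, time against time | Yes, but not by cohort |

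The endpoint comprises 7 analytes × 3 times = 21 fu quantities. None is the response in an impaired-versus-healthy model. The displays titled for unbound parameters (Tables 3.4 and 3.6, Listing 42) name daprodustat only, so 6 of 7 analytes are outside them.

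**2. The plan's own precision figure**

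Inputs from Protocol 10.2.1 are 8 per cohort and log-scale SDs of 0.402 (AUC) and 0.278 (Cmax). The 90% CI around a ratio of 1 is exp(± t(0.95, 2n − 2) × SD × √(2/n)), with t(0.95, 14) = 1.7613 and √(2/8) = 0.5.

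- AUC: 1.7613 × 0.402 × 0.5 = 0.354, giving 0.702 to 1.425. The protocol states 0.70 to 1.43.
- Cmax: 1.7613 × 0.278 × 0.5 = 0.245, giving 0.783 to 1.277. The protocol states 0.78 to 1.28.

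The formula matches the plan's method.

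**3. The same formula for log(fu)**

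The documents give no SD for fu, so the SD is an assumed range. The evaluable n of 6 and 4 are also assumptions, to allow for sparse data.

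| n per cohort | t | SD 0.2 | SD 0.3 | SD 0.4 |
|---|---|---|---|---|
| 8 | 1.7613 | 0.84 to 1.19 | 0.77 to 1.30 | 0.70 to 1.42 |
| 6 | 1.8125 | 0.81 to 1.23 | 0.73 to 1.37 | 0.66 to 1.52 |
| 4 | 1.9432 | 0.76 to 1.32 | 0.66 to 1.51 | 0.58 to 1.73 |

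**4. Can the fu ratio be recovered from free and total AUC?**

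For daprodustat, log free AUC = log AUC + log fu. The free-AUC ratio divided by the total-AUC ratio is therefore the fu ratio, if the same participants contribute to both. Its CI cannot be recovered from the two reported CIs, because the SD of log free AUC is √(0.402² + s² + 2ρ × 0.402 × s), where s is the log-fu SD and ρ its correlation with log AUC. With s = 0.3 (assumed):

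- ρ = −0.5: SD 0.362, free-AUC CI 0.73 to 1.38
- ρ = 0.5: SD 0.610, free-AUC CI 0.58 to 1.71

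The fu CI is 0.77 to 1.30 in both cases. The metabolites have no free parameters, so this route is closed for them.

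**5. Which fu defines free exposure**

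Let R(t) be the impaired:healthy geometric mean fu ratio at time t. Switching from the 3 h to the 24 h value multiplies the free-exposure ratio by R(24 h)/R(3 h). An assumed quotient of 1.0, 1.1 or 1.25 changes it by 0%, 10% or 25%.

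**6. Cost in chance findings**

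With no true binding effect, 21 × 0.10 = 2.1 of the 21 unadjusted 90% CIs are expected to exclude 1, whatever the correlation between them. For daprodustat alone it is 3 × 0.10 = 0.3. If Part 2 is run, there are 42 CIs and 4.2 expected exclusions.

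**The case against.** The strongest reply is that the general wording already covers fu. SAP 2.3 promises mean ratios with 90% CIs for the PK parameters and sets aside only %AUCex and Tmax. SAP 10.4.3 names only those two as not log-transformed. Protocol 10.4.1.1 has the same exception, and Table 4 lists fu as a derived parameter. The short lists are plainly not exhaustive, since the ANOVA and ANCOVA text and 10.4.3 also omit the free parameters that are modelled anyway. This does not close the gap. Protocol 10.4.1 spells out the log-transformed set as AUC(0-t), AUC(0-∞), Cmax and half-life. The notes to Tables 3.7 and 3.8, which do correct the short lists by adding the free parameters, still omit fu. If fu was intended, no model or display carries it out, and the same fix applies.

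It is also fair to say that the plan gives more than nothing. A descriptive fu summary could appear in Tables 3.3 to 3.6 under the protocol's general wording on derived parameters. Tables 3.1 and 3.2 allow approximate fu values for every analyte. Listings 39 and 40 hold the individual total and unbound concentrations. These permit later calculation, but none is a pre-specified ratio with a CI.

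Three further points stand as limits. The endpoint applies only as far as the data allow, no hypothesis is tested, and SAP 2.3 puts daprodustat Cmax and AUC first, so a descriptive plan for sparse data would be defensible if it were stated. SAP 2.3 assigns %AUCex and Tmax to descriptive summary, but makes no such assignment for fu. At 4 per cohort and an SD of 0.4, a metabolite ratio would say little. The GSK non-compartmental guidance cited in the SAP (GUI_51487) was not available and may contain a rule for the fu time point.

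**Conclusion.** The concern holds and should be fixed before the analysis. None of the 7 analytes has fu in a planned impaired-versus-healthy model, so the second primary objective is left without an interval estimate. The count rests on the SAP text and display list alone. This is a missing estimate, not a broken commitment or an error-rate problem, and it does not touch the Part 2 decision.

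The precision figures describe what the added estimate could deliver and rest on the assumed log-fu SD. With 8 per cohort and an SD up to 0.4, the interval is no wider than the one the protocol accepts for AUC. The fu time point is a clarification only. It matters only if the impaired:healthy fu ratio differs between times, and it does not carry the finding.

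**What to change.** In SAP 7.2.1.2.2, 10.4.3 and the PK table list:

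1. Name fu, by analyte and time point (3, 12 and 24 h), in the by-cohort summaries.
2. Add log(fu) to the existing cohort ANOVA. Report the impaired:healthy geometric mean ratio with its 90% CI for daprodustat and, where data allow, each metabolite. Give the evaluable n per cohort and label the results as estimation only, without multiplicity adjustment.
3. State, before the analysis, which fu (one time point or an average) defines free AUC and free Cmax.

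Keep the paired t-test and Table 3.10 as the check on concentration dependence.

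The cost is SAP wording and at most 21 extra fits per study part, on values already derived, with no new samples. The drawback is up to 21 unadjusted ratios per part, some on sparse data.
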